# **3. KEY DEFINITIONS**

Index date: The date of initiation of the first cycle of InO.

**Baseline period**: Period from 6 months before index date to the index date. The closest observation recorded during the baseline period and closest to index date will be used as baseline data (when more than one observations are available).

**CR/CRi rate**: Number of patients who achieve complete remission/complete remission with incomplete hematologic recovery (CR/Cri) divided by the total number of patients completing treatment with InO (defined as patients with a recorded date of discontinuation of InO).

**Complete remission (CR)**: is defined as 5% bone marrow blasts, no evidence of disease in the bone marrow, and recovery of peripheral blood count (platelet count of >  $100 \times 109/L$  and absolute neutrophil count of >  $1 \times 109/L$ ).

**CR with incomplete count recovery (CRi)**: is defined as 5% bone marrow blasts and no evidence of disease in the bone marrow, but with incomplete recovery of peripheral blood count. Minimal residual disease (MRD) will be assessed at each participating institution by multicolor flow cytometry.

**MRD negativity r**ate: Proportion of patients in whom minimal residual disease (MRD)-negative status is observed, among patients in whom MRD negativity status has been assessed, at any time until the end of treatment with InO (defined as the date of recorded discontinuation of InO). OS: Time from index date to death.

**RFS:** Time from index date to the earliest date of the following events: death, progressive disease (including objective progression, relapse from CR/CRi, treatment discontinuation due to global deterioration of health status), or the start of new induction therapy or posttherapy haematopoietic stem cell transplantation (HSCT) without achieving CR/CRi.

**EMD**: Extramedullary disease is the presence of leukemic cell aggregates in the form of solid tumor outside that of bone marrow.i

LBL: lymphoblastic lymphoma, is a clonal hematopoietic stem cell disorder of B or T cell originii

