## 9.1. Study design /Setting

The study is classified as a Non-interventional study (NIS) secondary data collection- unstructured review with sites/investigators.

R/R B-cell ALL patients who are 18 years old at the time of InO initiation and those who received the drug outside of clinical trials will be evaluated.

Data will be collected retrospectively from patients hospital medical records (paper-based ) by members of the direct care team (investigators). We intend to have 7- 10 sites across India using InO monotherapy including patients with both private purchase and compassionate use to reach a cohort of approximately 55. If needed, more sites will be enrolled to meet the target cohort. Data will be reviewed and analyzed from all the sites.

Medical records will be reviewed to collect demographic, patient-related, disease-related, and clinical outcome data. These patients will be evaluated for response (CR/CRi), MRD status, duration of remission (DOR), Dosage patterns, Rate of transplant, Overall survival in all patients including Survival rate at 6 months and 12 months in transplanted patients & non transplanted patients, Relapse free survival (RFS), Rate of VOD (Total, during study treatment and post HSCT if any patient underwent HSCT), safety/tolerability, Other adverse effects (including hematological toxicities and raised liver enzymes), No of cycles to achieve MRD negativity in responders & CR/CRi in EMD/LBL.

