#### 9.1.4. Secondary endpoints

- MRD Negativity following initiation of Ino
- Number of cycles of InO needed to attain CR/CRi
- DOR
- Dosage pattern: InO doses, dose modifications, and the number of cycles of treatment;
- Concomitant medications
- Rate of transplant (No of patients who proceeded to transplant)
- Survival rate at 6 months & 12 months (transplanted patients & non transplanted patients, in both who achieved CR/CRi and MRD negativity)
- Cause of death
- Relapse-free-survival; in all patients and patients with or without follow-up HSCT.
- Rate of VOD (Total, during study treatment and post HSCT, if any patient underwent HSCT) in transplanted & non transplanted patients.
- Occurrence of Grade 3/4 treatment-related adverse events in lung/cardiac/kidney/liver etc following InO initiation; in all patients and patients with or without follow-up HSCT & hematological toxicities
- CR/CRi in EMD/LBL

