#### 9.2. Data sources

Data for this study will be collected through retrospective data collection from 7-10 sites for patients in India who received Inotuzumab for the indication of adult R/R B Cell ALL between the time period Feb'2017 – Feb'2022. Additional centers may be added at a later stage if the target sample size is not achieved.

Data will be collected in anonymized form on Paper/excel based CRF for the study. Participants will be identified in all study records by a unique participant identification number to allow data management queries to be resolved with reference to source medical records while preserving patient confidentiality.

Medical records will be reviewed from secondary data sources to collect demographic, patientrelated, disease-related, and clinical outcome data & AE's. These patients will be evaluated for response, duration of response (DOR), OS from the time of InO initiation till 6 months or 1 year of therapy and toxicity

Data to be verified in accordance with Protocol standards. Before obtaining the data from the selected sites across the nation, the necessary regulatory approval will be ensured.

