#### 9.7. Limitations of the research methods

- The medical records may not be available for each & every data points provided in the CRF, from the aspect of the clinician or the patient.
- Patients may be lost to follow-up due to the occurrence of AEs, lack of efficacy or other reasons.
- This could be due to censoring events, that is, information on time to outcome event may not available for all study participants. Patient/s in such cases will be marked as "censored" when such information on time to event is not available due to loss to follow-up or non-occurrence of outcome events before the end of the study.
- For such patients (censored because of lost to follow-up due to the occurrence of AEs, lack of efficacy or other reasons), the use of Kaplan-Meier curves will be obtained as estimates of median OS, RFS and time to CR/Cri taking into account patients' attrition.
- The interpretation of data collected retrospectively will be dependent on the completeness and quality of the medical records and the reliability of the abstraction of data from the medical records. However, Source data verification (SDV) will be employed to identify and correct abstraction errors.

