# 2.1 STUDY DESIGN

The study is classified as a Non-interventional study (NIS) secondary data collectionunstructured review with sites/investigators.

R/R B-cell ALL patients who are  $\geq 18$  years old at the time of InO initiation and those who received the drug outside of clinical trials will be evaluated.

Data will be collected retrospectively from patients hospital medical records (paper-based) by members of the direct care team (investigators). We intend to have 7-10 sites across India using InO monotherapy including patients with both private purchase and compassionate use to reach a cohort of approximately 55 patients. If needed, more sites will be enrolled to meet the target cohort. Data will be reviewed and analyzed from all the sites.

Medical records will be reviewed to collect demographic, patient-related, disease-related, and clinical outcome data. These patients will be evaluated for response (CR/CRi), MRD status, duration of remission (DOR), dosage patterns, rate of transplant, survival time for all patients including survival rate at 6 months and 12 months in transplanted patients & non transplanted patients, Relapse free survival (RFS) time, Rate of veno-occlusive disease (VOD) (total during study treatment and post HSCT if any patient underwent HSCT), safety/tolerability, Other adverse effects (including hematological toxicities and raised liver enzymes), Number of cycles to achieve MRD negativity in responders & CR/CRi in Extramedullary disease / lymphoblastic lymphoma (EMD/LBL).

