# 4.1 FULL ANALYSIS SET

The restrospective available record of all Relapsed/Refractory B Cell Acute lymphoblastic leukemia adult patients satisfying specified inclusion and exclusion criteria will be the full analysis set.

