# 7.2 STATISTICAL ANALYSES

The distribution demographics variables like age and sex will be summarized by mean  $\pm$ SD and frequency (%) respectively. The prevalence of complete remission or complete remission with incomplete hematological recovery following treatment with InO will be reported with 95% confidence interval. Further these prevalence will be estimated for the

number of salvage therapies  $(0, 1, \ge 2)$  received before InO initiation.6 months or 12 months restricted mean remission free time will be estimated with 95% CI for both complete remission or complete remission with incomplete hematological recovery. The Kaplan-Meier curves of remission free survival will be drawn if a sufficient representation observed across the number of salvage therapies  $(0, 1, \ge 2)$  received before InO initiation. The restricted mean remission free time with 95% CI will be estimated for categories of number of salvage therapies. Restricted mean/median survival time will also be estimated with 95% CI. The Kaplan-Meier overall survival curve will also be drawn.

Other secondary endpoints like MRD negativity following initiation of InO or dosage pattern, concomitant medications, cause of death , occurrence of Grade 3/4 treatment-related adverse events in lung/cardiac/kidney/liver etc. following InO initiation and CR/CRi in EMD/LBL will also summarized by frequency and percentage and dration of response(DOR), no of patients who proceeded to transplant, total during study treatment and post HSCT will be summarized my median and interquartile range. restricted relapse-free-survival time will also be estimated with 95% CI if data permits for all patients and patients with or without follow-up HSCT.

Due to non-probability sampling technique, the extrapolation of the results will be restricted to the population that matches with sample characteristics only. Magnitude of the measure of any characteristics will be prioritised over statistical interpretation. However, interpretation of the result will be in a qualitative sense even though the related feature is compared numerically owing to descriptive nature of the study.

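### The listed 6- and 12-month survival endpoint, read literally, covers only patients with CR/CRi and MRD negativity, which conflicts with the all-patient survival in the design sections; no table settles which applies

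*Protocol*

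**What the plan says.** The secondary endpoint list in Protocol 9.1.4 contains "Survival rate at 6 months & 12 months (transplanted patients & non transplanted patients, in both who achieved CR/CRi and MRD negativity", and SAP 5 repeats it. The secondary objective in SAP 2.2 has the same responder qualifier but no time points. In all three lists, the neighbouring items on relapse-free survival and Grade 3/4 events expressly include all patients; the survival item does not.

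The design sections differ. Protocol 9.1 plans "Overall survival in all patients including Survival rate at 6 months and 12 months in transplanted patients & non transplanted patients", and SAP 2.1 plans "survival time for all patients including survival rate at 6 months and 12 months in transplanted patients & non transplanted patients". Neither attaches a response condition. Both give the 6- and 12-month rates by transplant status and name no pooled rate.

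Other places also point to all patients:
- Protocol 3 defines "OS: Time from index date to death", the index date being the start of the first InO cycle.
- Protocol 9.7 says that "the use of Kaplan-Meier curves will be obtained as estimates of median OS, RFS and time to CR/Cri".
- SAP 4.1 has a single analysis set: eligible patients "satisfying specified inclusion and exclusion criteria will be the full analysis set".
- SAP 7.2 states that "The Kaplan-Meier overall survival curve will also be drawn" and plans restricted mean or median survival time.

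The output lists in SAP 7.2.2 and SAP 8 include restricted mean overall survival. Neither lists a survival rate at 6 or 12 months, in any population.

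**The concern.** The study aim (Protocol 8, SAP 2.2) is to describe clinical outcomes among patients treated with InO in practice. CR/CRi and MRD negativity are reached after the index date, so a patient in the restricted set must have lived long enough to respond and be tested. If survival is still counted from the index date, early deaths without response are left out and the rate is too high as a description of the treated cohort. The protocol's own background (section 7) names CR and MRD negativity among the predictors of better survival, so the expected direction is upward.

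Two further features widen the selection. Protocol 3 counts MRD negativity only among patients assessed for it, and SAP 6 rules out imputation, so a responder without an MRD result may also drop out of the restricted set.

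At stake is which rate gets reported. Two analysts could follow the documents and give different populations under the same endpoint name, and a responder-only rate would invite comparison with the all-patient survival figures in the background.

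**Working it through.** The plan states no expected 6- or 12-month survival rate, so there is no figure to reproduce. What follows only illustrates the size.

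**Inputs** (Protocol 7, InO arm of the cited phase 3 trial): response 81%; MRD negativity among responders 78%; median overall survival 7.7 months; 2-year survival 23% on longer follow-up. Sample size: about 55 in Protocol 9.3, changed to 32 by the administrative change letter. Survival of the excluded patients is not in the documents and is varied.

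**Share retained.** p = 0.81 × 0.78 = 0.632, so 0.368 are excluded. That is about 20 of 32 kept and 12 left out, or 35 and 20 of 55.

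**All-patient survival.** Exponential with median 7.7 months, S(t) = exp(−ln 2 × t / 7.7): S(6) = 0.583 and S(12) = 0.340.

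**Restricted-set survival.** From S_all = p × S_kept + (1 − p) × S_excl, S_kept = (S_all − 0.368 × S_excl) / 0.632.

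| Median of excluded patients (assumed) | 6 months: kept set, excess | 12 months: kept set, excess |
|---|---|---|
| 7.7 months (same as all patients) | 58.3%, 0 points | 34.0%, 0 points |
| 5 months | 66.9%, 8.6 | 42.7%, 8.7 |
| 4 months | 71.6%, 13.4 | 46.5%, 12.5 |
| 3 months | 77.7%, 19.4 | 50.1%, 16.1 |
| 2 months | 84.9%, 26.7 | 52.8%, 18.9 |
| None alive at that time (upper bound) | 92.2%, 34.0 | 53.7%, 19.8 |

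**Sensitivity to the curve.** A Weibull curve through 7.7 months and 23% at 24 months gives all-patient rates of 56% and 39%, with upper bounds of 32 and 23 points.

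**Who is excluded.** Non-responders are 19% of patients. Responders who are not MRD-negative are 0.81 × 0.22 = 17.8%, so 0.178 / 0.368 = 48% of the excluded group did respond. If those responders have the all-patient median of 7.7 months and only the 19% have a median of 2 to 4 months (both assumptions), the excess is 0.19 × (S_all − S_NR) / 0.632, where S_NR is survival of the non-responders:
- 6 months: 0.19 × (0.583 − 0.125) / 0.632 = 0.138 at a median of 2 months; 0.19 × (0.583 − 0.354) / 0.632 = 0.069 at 4 months.
- 12 months: 0.19 × (0.340 − 0.016) / 0.632 = 0.097 at 2 months; 0.19 × (0.340 − 0.125) / 0.632 = 0.065 at 4 months.

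That is roughly 7 to 14 points at 6 months and 6 to 10 at 12 months.

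**If the condition is CR/CRi only** (p = 0.81), the upper bounds are 0.583 / 0.81 − 0.583 = 0.14 and 0.340 / 0.81 − 0.340 = 0.08.

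**The case against.** The strongest reply is that the plan does cover non-responders. A reader of the endpoint list alone might infer that they are left out of survival altogether. The documents do not support that: both design sections plan survival in all patients, Protocol 9.2 evaluates "OS from the time of InO initiation till 6 months or 1 year of therapy and toxicity" without a response condition, and the SAP plans an unrestricted overall survival curve with restricted mean or median survival. This stands, and it limits the point to the listed 6- and 12-month rate.

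The qualifier can also be read as an added breakdown (patients with CR/CRi, and patients with MRD negativity) rather than as the sole population. That is possible, and it would agree with the design sections. But the text does not say so and no table shell decides it. A responder breakdown counted from the index date would also carry the same bias if read as describing treated patients.

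A reader might further infer that the reported rate will be far above that of the cohort, by giving the whole excluded 37% a median of 2 to 4 months (13.4 to 26.7 points at 6 months, 12.5 to 18.9 at 12). The documents contain no survival figure for these patients, and nearly half of them would be responders, so that assumption is hard to defend. The trial's figures may also not transfer: patients who did not complete one cycle are ineligible here (Protocol 9.1.2), so some of the earliest failures are already outside the cohort.

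Finally, this is one of twelve secondary endpoints in a descriptive study with no hypothesis, to be interpreted qualitatively (SAP 7.2). That bears on importance, not on whether the wording conflicts.

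**Conclusion.** The point holds as a conflict over the survival population and a missing output. Protocol 9.1.4, SAP 2.2 and SAP 5, read literally, condition survival on later response; Protocol 9.1 and SAP 2.1 do not; and neither SAP table list contains a 6- or 12-month rate. The literal endpoint is biased upward for the treated cohort whenever excluded patients survive worse, as the protocol's background implies.

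The size cannot be fixed from the documents. On the cited trial's figures with exponential survival, it runs from 0 to at most 34 points at 6 months and from 0 to at most 20 at 12 months. It is about 7 to 14 and 6 to 10 points if only non-responders do badly, under the assumptions above. The zero end requires excluded patients to survive as well as the rest.

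For scale, an approximate 95% interval (Wilson, 19 of 32 alive, no censoring) runs from 42% to 74%. The bias may be smaller than the sampling error, but it is systematic and the interval would not reveal it. Importance is moderate: a secondary endpoint, with all-patient overall survival already planned.

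**What to change.** Reconcile Protocol 9.1.4, SAP 2.2 and SAP 5 with Protocol 9.1 and SAP 2.1. Suggested wording for the main survival summary: *Kaplan-Meier OS at 6 and 12 months from first InO dose, with 95% CI, in all patients in the full analysis set.* Add that row to the lists in SAP 7.2.2 and SAP 8.

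Keep the CR/CRi and MRD-negative results as supplementary. State whether they are two groups or one joint condition. Use a landmark analysis or count time from the date of response, and show the number of patients excluded beside each result.

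The cost is endpoint wording and one table row read from a curve that is already planned. The survival figure will probably look less favourable than a responder-only rate.

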# 11. MANAGEMENT AND REPORTING OF ADVERSE EVENTS/ADVERSE REACTIONS

- All AEs will be captured from the medical records.
- Number of Participants Who Experienced a Documented Diagnosis of Veno-occlusive Disease (VOD)/Sinusoidal Obstruction Syndrome (SOS) Post InO Treatment.
- Number of Participants Who Survived Following Treatment For Documented Diagnoses of Venoocclusive Disease (VOD)/Sinusoidal Obstruction Syndrome (SOS).
- Number of Participants With Interrupted InO Treatment Due to VOD/SOS.
- Number of Participants Who Experienced Grade 3 and Grade 4 (Lung/Cardiac/Kidney/Liver) Treatment-Related Adverse Event (TRAE) Following InO initiation.
- All hematological AEs: Neutropenia, febrile neutropenia, and thrombocytopenia
- Being NIS secondary data collection— This study involves retrospective patients treated with InO for R/RB-cell ALL data that exist as unstructured data by the time of study start or a combination of existing unstructured data, which will be converted to structured form during the implementation of the protocol solely in an excel using CRF template.
- It is not possible to link (ie, identify a potential association between) a particular product and medical event for any individual. Thus, the minimum criteria for reporting an AE (ie, identifiable patient, identifiable reporter, a suspect product, and event) cannot be met.

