# **12. SAFETY REPORTING**

- This study protocol requires human review of patient-level unstructured data; unstructured data refer to verbatim medical data, including text-based descriptions and visual depictions of medical information, such as medical records, images of physician notes, neurological scans, x-rays, or narrative fields in a database. The reviewer is obligated to report AEs with explicit attribution to any Pfizer drug that appear in the reviewed information (defined per the patient population and study period specified in the protocol). Explicit attribution is not inferred by a temporal relationship between drug administration and an AE but must be based on a definite statement of causality by a healthcare provider linking drug administration to the AE.
- The requirements for reporting safety events on the NIS adverse event monitoring (AEM) Report Form to Pfizer Safety are as follows:
  - All serious and non-serious AEs with explicit attribution to any Pfizer drug that appear in the reviewed information must be recorded on the case report form & AE reporting form and reported, within 24 hours of awareness, to Pfizer Safety using the NIS AEM Report Form.
  - Scenarios involving drug exposure, including exposure during pregnancy, exposure during breast feeding, medication error, overdose, misuse, extravasation, lack of efficacy, and occupational exposure associated with the use of a Pfizer product must be reported, within 24 hours of awareness, to Pfizer Safety using the NIS AEM Report Form.
  - For exposure during pregnancy in studies of pregnant women, data on the exposure to InO during pregnancy, are not reportable unless associated with serious or non-serious adverse events.
  - For these AEs with an explicit attribution or scenarios involving exposure to a Pfizer product, the safety information identified in the unstructured data reviewed is captured in the Event Narrative section of the report form, and constitutes all clinical information known regarding these AEs. No follow-up on related AEs will be conducted.

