#### This PACL makes the following changes:

	izer		
3	6. MILESTONES	Change in Milestones- Planned Date	Start of data collection - 13 February 2023 End of data collection - 05 July 2023 Final Study report - 10 October 2023
4	9. RESEARCH METHODS 9.3 Study size	Sample size changed to 32 subjects	Sample size is changed to 32 subjects
5	11. MANAGEMENT AND REPORTING OF ADVERSE EVENTS/ADVERSE REACTIONS 12. SAFETY REPORTING	To clarify the adverse event reporting requirements for structured and unstructured data components. Also, to correct the inconsistency with the protocol template language.	The last 2 paragraphs of Section 11 should be moved to the beginning of Section 12, Adding a subheading "12.1 Structured Data Analysis", under which the 2 paragraphs are pasted and revised. In addition, add a second sub- heading "12.2 Human Review of Unstructured Data" above the original content of Section 12.

In the event that this protocol requires substantial changes that apply globally to all sites in the future or regulatory authorities request that these changes be incorporated into an updated protocol, the administrative changes described in this letter will be incorporated into the amended protocol.

Please inform your institutional review board/ ethics committee of these changes, as required.

Sincerely, [name]

cc: NI study master file

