# 7.2.2 Analyses of endpoint

The following tables and figures will be generated for the analysis of endpoints.

- 1. The distribution of demographics characteristics (mean ±SD for age and frequency and percentage for sex)
- 2. MRD negativity following initiation of InO (frequency and percentage)
- 3. Dosage pattern (frequency and percentage)
- 4. Cause of death (frequency and percentage)
- 5. Occurrence of Grade 3/4 treatment-related adverse events in lung/cardiac/kidney/liver etcfollowing InO initiation (frequency and percentage)
- 6. CR/CRi in EMD/LBL (frequency and percentage)
- 7. Duration of response (DOR) (Median and Interquartile Range (IQR))
- 8. No of patients who proceeded to transplant (Median and IQR)
- 9. Total during study treatment and post HSCT (Median and IQR)
- 10. Restricted remission free time with 95% confidence interval for both complete remission and complete remission with incomplete hematological recovery.

- 11. Restricted remission free time with 95% confidence interval for both complete remission and complete remission with incomplete hematological recovery stratified by the number of salvage therapies  $(0, 1, \ge 2)$  received before InO initiation
- 12. Restricted mean overall survival time with 95% CI.
- 13. Restricted relapse-free-survival with 95% CI for all patients and patients with or without follow-up HSCT.

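### The Grade 3/4 organ-toxicity endpoint and its only table count treatment-related events, but no rule says how relatedness is decided and no all-cause table is planned

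*Protocol*

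**What the plan says.** Protocol 9.1.4 lists as a secondary endpoint "Occurrence of Grade 3/4 treatment-related adverse events in lung/cardiac/kidney/liver etc following InO initiation", for all patients and by whether a transplant followed, together with haematological toxicities. Protocol 11 repeats the restriction, counting patients with a Grade 3 or 4 "Treatment-Related Adverse Event (TRAE) Following InO initiation". SAP Section 5 copies the endpoint. SAP 7.2.2 item 5 and Section 8 Table 5 give its only output, "Occurrence of Grade 3/4 treatment-related adverse events in lung/cardiac/kidney/liver" and so on, as frequency and percentage.

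Other safety items carry no such filter. Protocol 11 states that "All AEs will be captured from the medical records", counts VOD/SOS on a documented diagnosis, and lists all haematological events.

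Two further passages bear on attribution:

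- Protocol 11 also says "It is not possible to link (ie, identify a potential association between) a particular product and medical event for any individual". The administrative change letter deals with this text: "The last 2 paragraphs of Section 11 should be moved to the beginning of Section 12". It is to be revised there under a new heading 12.1 for structured data, and the existing Section 12 text goes under 12.2 for human review of unstructured data. The stated reason is "To clarify the adverse event reporting requirements for structured and unstructured data components".
- Protocol 12 says that explicit attribution "must be based on a definite statement of causality by a healthcare provider linking drug administration to the AE", and that timing alone is not enough.

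SAP 5.2 (safety endpoints) and 7.2.1 (safety analyses) are marked not applicable. SAP Appendix A1.2 (further endpoint definitions) says none. SAP 6 analyses available data only, without imputation.

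**The concern.** A treatment-related count needs a causal judgement for every event. Here InO was started between February 2017 and February 2022, and the change letter puts data collection between February and July 2023. A judgement of relatedness is therefore either one that a clinician charted at the time or one that the abstracting investigator makes later. The plan does not choose between the two, so sites may differ.

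Protocol 9.1 lists safety and tolerability among the outcomes, and the SAP confirms that there is a single group. With no comparator, nothing offsets a difference in attribution habits. The problem is sharpest in the split by transplant status that 9.1.4 asks for, because a lung or liver event after transplant has several possible causes. A reader of the report could not tell a low toxicity rate from sparse charting.

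**Working it through.** The plan states no toxicity rate, attribution share or precision target for this endpoint, so there is no figure of its own to reproduce. The check has three parts.

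**1. Is relatedness defined anywhere for this endpoint?**

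| Place | What it gives |
|---|---|
| Protocol 9.1.4, 11 | the restriction, with no rule |
| Protocol 12 | a causality standard, for reports to the sponsor's safety unit |
| SAP 5.2, 7.2.1, A1.2 | not applicable, or none |
| SAP 6 | available data only, with nothing on unrecorded relatedness |

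The decision maker, the rule and the handling of unknowns are all missing.

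**2. Which adverse events reach a table?** Of the 13 tables in SAP Section 8, only Table 5 plainly reports adverse events. It omits the haematological toxicities and the transplant split that 9.1.4 attaches to the endpoint. Table 9 looks like the VOD line of 9.1.4, but it does not name VOD. No table covers haematological events, and none gives all-cause Grade 3/4 events.

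**3. How much could the filter matter?** Let N be the number of patients, p the proportion with at least one all-cause Grade 3/4 organ event, and f the share of those patients with at least one such event counted as treatment-related.

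- Reported count = N × p × f, rounded. Reported rate = count / N, with a Clopper-Pearson 95% interval.
- N = 32 comes from the change letter. The values of p and f are assumptions, since the documents give neither.

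| p | f | N × p × f | Reported | 95% CI |
|---|---|---|---|---|
| 40% | 100% | 12.8 | 13/32 = 41% | 24–59% |
| 40% | 75% | 9.6 | 10/32 = 31% | 16–50% |
| 40% | 50% | 6.4 | 6/32 = 19% | 7–36% |
| 40% | 25% | 3.2 | 3/32 = 9% | 2–25% |
| 20% | 100% | 6.4 | 6/32 = 19% | 7–36% |
| 20% | 50% | 3.2 | 3/32 = 9% | 2–25% |

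Two rows give the same result, 6/32: p = 40% with half attributed, and p = 20% with all attributed. The planned table cannot separate them, whereas an all-cause column would.

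The handling of unknowns matters as well. Suppose 13 patients have an event, 6 are charted as related, and the other 13 − 6 = 7 have no recorded relatedness. Counting unknown as unrelated gives 6/32 = 19%. Dropping the 7 as missing gives 6/25 = 24%. Counting unknown as related gives 13/32 = 41%. SAP 6 does not say which applies.

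**The case against.** The strongest reply is that treatment-related toxicity is a legitimate descriptive target. A related-only count lies at or below the all-cause count by definition, and that gap alone is not bias. Some all-cause events are due to the disease or the transplant and should not count. With no rule, attribution error could also go either way, since an abstractor may over-attribute. All of this stands. It limits the point to an undefined quantity and a possible shortfall against all-cause toxicity.

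Three stronger readings are tempting, and the documents do not support them.

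- *Section 12 forbids inferring relatedness for the endpoint.* Its standard governs what is reported to the sponsor's safety unit within 24 hours. It also has explicitly attributed events entered on the case report form, so an abstractor might borrow it, but nothing makes it the endpoint definition. Investigators from the direct care team do the abstraction, and their own judgement is neither required nor excluded.
- *The protocol declares its own endpoint impossible.* The sentence on linkage leads to a conclusion about minimum criteria for reporting an event. The change letter moves it under structured data, while this study reads unstructured charts. Some ambiguity remains: the revised wording is not shown, and the adjoining paragraph, moved with it, describes converting chart data to structured form in a spreadsheet. That calls for reconciliation and does not prove a contradiction.
- *All toxicity is filtered by causality.* VOD/SOS and haematological events are not filtered in Section 11.

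**Conclusion.** The point holds for the Grade 3/4 organ-toxicity endpoint. Its only table is restricted to treatment-related events, relatedness is undefined, and no all-cause table is planned although all events are to be captured. The reported rate may depend on site practice and may understate all-cause toxicity.

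The size cannot be stated. At N = 32 and an assumed p of 40%, the reported rate runs from 41% (full attribution) to 9% (a quarter attributed). With full attribution there is no shortfall. A reader might infer that events will certainly be undercounted, or that a given share will be lost. Neither follows: any such share is just one minus an assumed f, and it treats every all-cause event as one that ought to be called related.

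This is a descriptive secondary endpoint, so the change is a worthwhile, inexpensive improvement. It does not affect the primary endpoint.

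**What to change.** In SAP 7.2, 7.2.2 item 5 and Section 8 Table 5, and correspondingly in protocol 9.1.4:

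- Beside the treatment-related column, add all-cause Grade 3/4 events after InO initiation by organ class, overall and by transplant status.
- Add haematological events to the same table.
- State who judges relatedness and by what rule, and show unknown relatedness as its own category.
- Reconcile the sentence on linkage, now assigned to 12.1, with the treatment-related endpoint, and show its revised wording.

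The cost is some extra columns and rows built from events that protocol 11 already has captured. The downside is a higher reported toxicity, some of it related to disease or transplant. Keeping the treatment-related column beside it lets the reader see both.
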